### 6.1.4 DEFINITION OF DOSE-LIMITING TOXICITY

Number of Patients with DLT at a Given Dose Level	Escalation Decision Rule	
0 out of 3	Enter 3 patients at the next dose level.	
≥ 2	Dose escalation will be stopped. This dose level will be declared the maximally administered dose <highest administered="" dose="">. Three (3 additional patients will be entered at the next lowest dose level if or 3 patients were treated previously at that dose.</highest>	
1 out of 3	
 
Enter at least 3 more patients at this dose level.
 
If 0 of these 3 patients experience DLT, proceed to the next dose level.
 
If 1 or more of this group experience DLT, then dose escalation is stopped, and this dose is declared the maximally administered dose. Three (3) additional patients will be entered at the next lowest dose level if only 3 patients were treated previously at that dose.
 
	
≤ 1 out of 6 at highest dose level below the maximally administered dose	This is generally the recommended phase II dose. At least 6 patients must be entered at the recommended phase II dose.	

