# 9.4.2 ANALYSIS OF THE PRIMARY ENDPOINT(S)

For the dose escalation portion, a minimum of two subjects and a maximum of 18 subjects will be enrolled. There will be three dose levels in the dose escalation portion. MTD is defined as the highest dose level with the probability of DLT less than 33% (DLT events are defined in Section 6). The DLT observation window will be until confirmation that the donor cells have been rejected (ANC ≥ 500/microL AND confirmation of either bone marrow donor chimerism <5% or donor blood CD3+ chimerism <5%) OR within 56 days following NE-DLI, whichever occurs first. Per the traditional 3+3 schema, up to three patients may be enrolled concurrently and treated at the same dose level. The first three patients will be treated at dose level 1. For each dose level, if none of three patients experiences a DLT, we will escalate to the next dose level until reaching dose level 3. For each dose level, if one of the three patients experiences a DLT, we will enroll three additional patients and treat at the same dose level. In this case, if none of these additional three patients experiences a DLT, we will escalate the dosage to next level until reaching dose level 3. For each dose level, if two or more patients among six enrolled patients experience a DLT, or two or more patients in the three patient cohort experience DLT, the dosage level exceeds the MTD and the previous dose level will be declared as the MTD. If the first dose level exceeds the MTD, the study will be suspended. If no subjects experience a DLT at any dose level, the MTD will be level 3 (5 x 10^7 CD4+ T cells/kg). Similarly, if exactly one of six patients enrolled at dose level 3 experiences a DLT, then the MTD will be dose level 3. All patients in a dose level must be observed through the DLT window prior to enrolling patients at a higher dose level.

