# 9.4.3 ANALYSIS OF THE SECONDARY ENDPOINT(S)

The RP2D is defined as the dose level selected to be evaluated in the expansion cohort or future phase II studies and will be equivalent to the MTD determined in the Phase 1b portion of the study. Once we determine the RP2D level, we will enroll 10 additional eligible patients and treat with the RP2D level. The goal for this expansion cohort is to evaluate the safety and tolerability for patients who will be treated with NE-DLI in the RP2D dose level, and to evaluate the preliminary efficacy estimate for the ORR. Including the dose escalation portion in which 3 or 6 enrolled patients will have been treated at the RP2D level, a total of at least 13 patients will be treated at the RP2D level. Based on previous data, (99) the complete response rate using microtransplantation was in the range of 36%-52% for MDS or AML from antecedent MDS patients. Hence, for the phase 2 portion, an ORR of 45% is considered clinically meaningful. With a sample size of 13 patients, if our ORR is 45%, the 95% CI (exact binomial) will be (18-74%); if the ORR is 50%, the 95% CI will be (22-78%). The response rates, including ORR and hematologic response by IWG 2006 criteria will be estimated via an exact binomial test with 95% confidence interval in combining patients treated at the RP2D dose level and the expansion cohort patients.

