#### 12.6 APPENDIX F: CRITERIA FOR DOSE ESCALATION

Dose escalation will occur if 0 out of the first 3 patients experience DLTs. Rules for dose escalation are as follows:

**0/3 DLTs:** Escalate the dose (dose levels 1-2), or halt dose escalation (dose level 3).

1/3 DLTs: Study an additional 3 patients. If an additional patient experiences a DLT, halt dose escalation. If no other patient experiences DLT (that is if 1/6 patients on dose level experiences DLT), escalate the dose (dose levels 1-2) or halt dose escalation (dose level 3).

2/3 DLTs: Halt dose escalation.

The decision to escalate the dose of donor peripheral blood cells and to enroll patients to the higher dose level may not be made until one of the following has occurred:

- 1. The first 3 patients have been fully evaluated for DLTs and none has experienced a DLT.
- 2. Six patients have been fully evaluated and only 1 has experienced a DLT.

The DLT observation window continues until the first of the following:

- 1. ANC > 500/microL AND confirmation the DLI has been rejected (either bone marrow donor chimerism <5% or donor blood CD3+ chimerism <5%)
- 2. Within 56 days following NE-DLI

If neither of these conditions has been met, patients will continue to be accrued to the current dose level. In the event that 0/3 patients experience DLT, accrual to the next higher dose level may proceed even if additional patients have been treated at the lower dose level and are not yet evaluable. However, if any of those patients experience DLT, accrual to the higher dose level will be suspended until a total of 6 patients have been treated and evaluated at the lower dose level. Further accrual to the higher dose level will not resume until the DLT incidence in the lower dose level is documented to be no greater than 1/6 patients. Accrual to the higher dose level will be stopped if the incidence of DLTs in the previous level exceeds 33% (for instance, if none of the first 3 patients experiences DLT, but the next 2, who were accrued during the observation period for the first 3 patients, do).

DLTs are defined as any of the following that is at least possibly attributable to the investigational treatment:

- 1. Grade 2-4 infusion toxicity
- 2. Grade 4 organ toxicity (as defined by NCI CTCAE v 5.0), not preexisting, not due to the primary malignancy, and not due to chemotherapy or infection

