- 3. Grade 3 organ toxicity that does not resolve within 14 days and which is not preexisting, not due to the primary malignancy, and not due to chemotherapy or infection
- 4. Grade 2-4 acute GvHD
- Delayed neutrophil recovery: ANC>500/μl does not occur within 56 days AND measurable donor chimerism is >5%
- 6. Grade 3-4 CRS; see Appendix for grading scheme)
- 7. Any Grade 5 reaction other than progressive disease.

If 2 or more of the first 6 patients on any dose level experience DLTs, accrual to the trial will be suspended and the sponsor of the IDE (the PI) will initiate a formal consultation with the FDA in order to determine whether the

CD8-depleted non-engrafting HLA antigen-mismatched unrelated donor lymphocyte infusion... Protocol <20042> Version 10 29 March 2023

observed toxicities are or are not attributable to the device. Subsequent accrual to the trial may resume only with permission from the FDA. Any questions or concerns as to the relationship of grade > 3 toxicities to use of the investigational device will be discussed with the appropriate FDA Clinical Review Staff.

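### The rule for declaring the MTD is stated two ways: Section 9.4.2 declares the dose below a failed level at once, while Section 6.1.4 first adds three patients there if only three were treated

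*Combined protocol and SAP*

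**What the plan says.** **Direct declaration.** Sections 4.3, 6.1.3 and 9.4.2 each say that with two or more DLTs in 3 or in 6 patients, "the dosage level exceeds the MTD and the previous dose level will be declared as the MTD". None of them calls for further patients at that previous level. Section 9.4.3 sets the RP2D equal to the MTD, counts 3 or 6 escalation patients at it, adds 10 expansion patients, and concludes that "a total of at least 13 patients will be treated at the RP2D level".

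**Backfill.** In the escalation table of Section 6.1.4, a failed level is the maximally administered dose, and three "additional patients will be entered at the next lowest dose level if only 3 patients were treated previously at that dose". (This wording is from the row for 1 DLT in 3. The row for two or more DLTs gives a matching instruction, but its condition is not fully legible in the copy reviewed.) The last row takes as the recommended dose, generally, the highest level below the failed one with at most 1 DLT in 6, and adds: "At least 6 patients must be entered at the recommended phase II dose".

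**Appendix F**, to which 4.1 and 9.4.1 refer for the 3+3 schema, says only that escalation halts. It is silent on backfill. It adds a step that 9.4.2 does not mention: "If 2 or more of the first 6 patients on any dose level experience DLTs, accrual to the trial will be suspended", and "Subsequent accrual to the trial may resume only with permission from the FDA".

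**Two smaller mismatches.**
- On opening the next level, 9.4.2 says "All patients in a dose level must be observed through the DLT window prior to enrolling patients at a higher dose level". Appendix F says that after 0/3 "accrual to the next higher dose level may proceed even if additional patients have been treated at the lower dose level", with their DLT evaluation still incomplete.
- On the DLT window, 4.3 gives a fixed 56 days, and 4.4 uses 56 days in its duration estimate. Section 6.1.3 defers to 9.4.2. Section 9.4.2 and Appendix F use the earlier of 56 days or neutrophil recovery with confirmed rejection of the donor cells.

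**The concern.** A 3+3 design is defined by its decision rule, and here that rule fixes both the primary endpoint and the dose given to the expansion cohort. Take 0/3 DLTs at level 1 and 2/3 at level 2. Accrual is suspended for FDA consultation. When it resumes, 9.4.2 makes level 1 the MTD on the strength of 0/3, and the 10 expansion patients can start. Section 6.1.4 treats three more patients at level 1 first. If two of them have DLTs, level 1 stands at 2/6 and there is no MTD. The same data can therefore lead either to an expansion cohort or to a trial with no acceptable dose.

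The evidence behind the dose also differs. The exact one-sided 95% upper limit for the DLT rate is 63% after 0/3, against 39% after 0/6 and 58% after 1/6. The stated minimum at the RP2D, and the confidence interval built on it, depend on which rule applies.

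**Working it through.** **1. The plan's own figures.** The minimum at the RP2D is 3 + 10 = 13, and the maximum enrolment is 6 × 3 + 10 = 28. Clopper-Pearson limits with x = ORR × n (5.85 and 6.5 of 13) are 18.4-73.9% and 22.1-77.9%, which match the stated 18-74% and 22-78%.

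**2. The same quantities under 6.1.4.** Below a failed level the minimum is 6 + 10 = 16. The limits at n = 16 are 21-71% for an ORR of 45% and 25-75% for 50%. With whole counts, 6/13 gives 19-75% and 7/16 gives 20-70%. For one DLT, 1/13 gives 0.2-36% and 1/16 gives 0.2-30%. The 6.1.4 table does not clearly cover 0/3 at level 3, so 13 can still arise by that route.

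**3. How often the rules part.** For a level with DLT probability p:
- passes on three patients: a = (1-p)³
- passes on six: b = 3p(1-p)² × (1-p)³
- fails: f = 1 - a - b
- three backfill patients bring two or more DLTs: g = 1 - (1-p)³ - 3p(1-p)²

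The plan gives no DLT rates, so every curve below is an assumption. For rates of 5%, 15% and 30% at levels 1 to 3:

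| Level | a | b | f | g |
|---|---|---|---|---|
| 1 | 0.8574 | 0.1161 | 0.0266 | 0.0073 |
| 2 | 0.6141 | 0.1997 | 0.1862 | 0.0608 |
| 3 | 0.3430 | 0.1513 | 0.5057 | 0.2160 |

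- Rules diverge (a level fails and the one below has only three patients): a₁f₂ + (a₁+b₁)a₂f₃ = 0.8574 × 0.1862 + 0.9734 × 0.6141 × 0.5057 = 0.160 + 0.302 = 0.462.
- MTD changes: 0.160 × 0.0073 + 0.302 × 0.0608 = 0.001 + 0.018 = 0.020 after rounding.
- 0/3 at level 3: (a₁+b₁)(a₂+b₂)a₃ = 0.9734 × 0.8138 × 0.3430 = 0.272.

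The same enumeration on all five main curves, repeating the backfill one level down if a backfilled level reaches two DLTs:

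| DLT rates (%) | Rules diverge | MTD changes | Rise in P(no MTD) | 0/3 at level 3 | E[N] without / with backfill |
|---|---|---|---|---|---|
| 5, 15, 30 | 0.462 | 0.020 | 0.0013 | 0.272 | 10.7 / 12.1 |
| 10, 20, 40 | 0.533 | 0.039 | 0.0067 | 0.139 | 10.2 / 11.9 |
| 10, 25, 45 | 0.584 | 0.054 | 0.0092 | 0.090 | 9.9 / 11.8 |
| 5, 10, 20 | 0.287 | 0.006 | 0.0006 | 0.452 | 10.7 / 11.6 |
| 10, 35, 50 | 0.646 | 0.070 | 0.0136 | 0.045 | 9.1 / 11.2 |

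Seven further curves, from (1, 2, 5%) to (30, 40, 50%), widen the ranges:
- divergence: 0.03-0.74
- MTD change: 0-0.086
- rise in no MTD: 0-0.056
- 0/3 at level 3: 0.02-0.85

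**4. Can the expansion cohort stand in for the backfill?** Under 9.4.3 it opens only once the RP2D is fixed, and it is monitored by other rules. Section 6.1.4 calls for a discussion at 2 or more DLTs in 6. Section 9.4.4 holds enrolment at 2 in the first 3, or at 3 in 4-6. Neither is the at-most-1-in-6 test that 6.1.4 sets for naming the dose.

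**The case against.** The strongest reply is that 6.1.4 supplements 9.4.2. Section 9.4.2 does not exclude further patients, and it says that two or more DLTs among six at any level exceed the MTD, so a failed backfill reaches an outcome it already covers. This does not hold. After 0/3 and then 2/3, the instruction in 9.4.2 to declare the previous level would have to be set aside while three more patients are treated.

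The direct rule also appears three times and the backfill once, in a table whose surrounding text mentions consulting CTEP, a body with no other role in this single-site protocol. The backfill may be leftover template text. That bears on which rule to keep, but nothing in the plan says so. Section 10.1.5 refers to a data and safety plan, but that plan is to follow the protocol's own rules.

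Several points against its weight do stand:
- After 0/3, the first expansion look nearly repeats the backfill. Two DLTs in three give a Beta(3,6) posterior with a 0.68 probability that the rate exceeds 0.25, above the 0.65 threshold. What remains is the difference between hold-and-review and automatic demotion.
- Every diverging path first passes through the FDA consultation.
- The enumeration assumes exactly three patients at a level that passes on 0/3. Appendix F keeps accruing during evaluation, and at one patient per 5-6 weeks a fourth may be present, so the condition of only three patients would be met less often.
- The 9.4.3 floor of 13 does not by itself exclude a backfill.
- The secondary mismatches are minor. Following 9.4.2 on opening levels breaches neither text, and the FDA step can coexist with 9.4.2.

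**Conclusion.** The concern holds. The plan contains two decision rules for its primary endpoint that cannot both be followed when a level fails and the one below has three patients. It gives no precedence. On the assumed curves that situation is common, but a different declared dose is not. The chance of ending with no MTD rises by 0.06 to 1.4 percentage points on the main curves and by at most 5.6 over all twelve. The gain in precision from 16 rather than 13 patients is modest. This should be corrected because the conflict concerns how the primary result is reached and the remedy is cheap. It does not make the trial unsafe or its dose choice generally unreliable. The frequencies rest on assumed DLT rates and on exactly three patients at each level passed on 0/3. The textual conflict rests on neither.

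**What to change.** State one complete algorithm in 9.4.2 and replace the versions in 4.3, 6.1.3, 6.1.4 and Appendix F with cross-references.

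**Preferred, for the sponsor to confirm:** adopt the backfill, so that the MTD is the highest level with at most 1 DLT in 6. Say whether 0/3 at level 3 is also expanded to six. Then restate the minimum at the RP2D and its interval: 16 if six are always required, otherwise 13. The cost is up to three more patients at the RP2D. Expected phase 1 size rises by 0.9-2.1 patients on the main curves (0.1-2.4 over all twelve), from 9.1-10.7 to 11.2-12.1, or to 11.4-13.1 on the main curves if level 3 is also expanded. No level exceeds six, so the maxima of 18 and 28 hold.

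**Alternative:** if no backfill is intended, remove it and the six-patient minimum from the 6.1.4 table and keep 13. This costs wording only.

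Either way, keep the 9.4.2 rule on opening the next level and delete the early-opening permission in Appendix F. Align the window wording in 4.3 and 4.4 with 9.4.2, and refer from 9.4.2 to the suspension and FDA consultation in Appendix F.

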# 9.4.3 ANALYSIS OF THE SECONDARY ENDPOINT(S)

The RP2D is defined as the dose level selected to be evaluated in the expansion cohort or future phase II studies and will be equivalent to the MTD determined in the Phase 1b portion of the study. Once we determine the RP2D level, we will enroll 10 additional eligible patients and treat with the RP2D level. The goal for this expansion cohort is to evaluate the safety and tolerability for patients who will be treated with NE-DLI in the RP2D dose level, and to evaluate the preliminary efficacy estimate for the ORR. Including the dose escalation portion in which 3 or 6 enrolled patients will have been treated at the RP2D level, a total of at least 13 patients will be treated at the RP2D level. Based on previous data, (99) the complete response rate using microtransplantation was in the range of 36%-52% for MDS or AML from antecedent MDS patients. Hence, for the phase 2 portion, an ORR of 45% is considered clinically meaningful. With a sample size of 13 patients, if our ORR is 45%, the 95% CI (exact binomial) will be (18-74%); if the ORR is 50%, the 95% CI will be (22-78%). The response rates, including ORR and hematologic response by IWG 2006 criteria will be estimated via an exact binomial test with 95% confidence interval in combining patients treated at the RP2D dose level and the expansion cohort patients.

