#### **Secondary Endpoints:**

- Overall response rate according to the International Working Group (IWG) (see Appendix B).
- Overall survival.
- Progression-free survival.
- Hematologic response/improvement by IWG 2006 criteria for MDS patients and the IWG 2003 criteria for AML (1, 2).
- Occurrence of adverse events.
- Unexpected transplant complications (eg, graft-versus-host disease [GvHD]).

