#### 9.4 STATISTICAL ANALYSES

#### 9.4.1 GENERAL APPROACH

This is a phase 1b/2 study with dose escalation for determination of the MTD/RP2D of NE-DLI via a traditional 3+3 dose escalation schemaa followed by an expansion cohort for assessing safety profile and preliminary estimation of the overall response rate (ORR) (complete response and partial response based on International Working Group definition). Eligible patients will be treated with NE-DLI in the pre-transplantation setting.

9.4.1.	1 ANA	ALYSIS	PLAN
--------	-------	--------	------

<sup>a See Appendix F

Toxicity events for NE-DLI will be descriptively summarized at each dose level. The response rates, including ORR and hematologic response by IWG 2006 criteria will be estimated via an exact binomial test with 95% confidence interval in combining patients treated at the RP2D dose level and the expansion cohort patients. Overall survival, defined from date of treatment to date of death or censored at last follow-up date, will be estimated via Kaplan-Meier method (combining patients treated at the RP2D dose level and expansion cohort patients). Other outcomes such as independence from red blood cell transfusion or platelet transfusion for 56 consecutive days or more, occurrence of AE, unexpected transplant complications will be descriptively reported via summary statistics.

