## 12.2 APPENDIX B: RESPONSE CRITERIA ACCORDING TO THE INTERNATIONAL WORKING GROUP(1)

Category	Response criteria (responses must last at least 4 wk)		
Complete remission	Bone marrow: ≤ 5% myeloblasts with normal maturation of all cell lines*		
	Persistent dysplasia will be noted*†		
	Poripheral blood±		
	Hgb ≥ 11 g/dL		
	Platelets ≥ 100 × 10°/L		
	Neutrophils $\geq 1.0 \times 10^9 L^{\frac{1}{4}}$		
	Blasts 0%		
Partial remission	All CR criteria if abnormal before treatment except:		
	Bone marrow blasts decreased by ≥ 50% over pretreatment but still > 5%		
	Cellularity and morphology not relevant		
Marrow CR†	Bone marrow: ≤ 5% myeloblasts and decrease by ≥ 50% over pretreatment+		
	Peripheral blood: if HI responses, they will be noted in addition to marrow CR+		
Stable disease	Failure to achieve at least PR, but no evidence of progression for > 8 wks		
Failure	Death during treatment or disease progression characterized by worsening of cytopenias, increase in percentage of bone		
	marrow blasts, or progression to a more advanced MDS FAB subtype than pretreatment		
Relapse after CR or PR	At least 1 of the following:		
	Return to pretreatment bone marrow blast percentage		
	Decrement of ≥ 50% from maximum remission/response levels in granulocytes or platelets		
	Reduction in Hgb concentration by ≥ 1.5 g/dL or transfusion dependence		
Cytogenetic response	Complete		
	Disappearance of the chromosomal abnormality without appearance of new ones		
	Partial		
	At least 50% reduction of the chromosomal abnormality		
Disease progression	For patients with:		
	Loss than 5% blasts: ≥ 50% increase in blasts to > 5% blasts		
	5%-10% blasts; ≥ 50% increase to > 10% blasts		
	10%-20% blasts: ≥ 50% increase to > 20% blasts		
	20%-30% blasts: ≥ 50% increase to > 30% blasts		
	Any of the following:		
	At least 50% decrement from maximum remission/response in granulocytes or platelets		
	Reduction in Hgb by ≥ 2 g/dL		
	Transfusion dependence		
Survival	Endocints:		
Service of the servic	Overall: death from any cause		
	Event free: failure or death from any cause		
	PFS: disease progression or death from MDS		
	DFS: time to relapse		
	Cause-specific death: death related to MDS		

Deletions to IWG response criteria are not shown.

To convert hemoglobin from grams per deciliter to grams per liter, multiply grams per deciliter by 10.

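### sAML response criteria: the analysis text drops IWG 2003 for hematologic response, and ORR rests on an appendix that holds MDS criteria only

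*Combined protocol and SAP*

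**What the plan says.** Two secondary endpoints are involved. The lists in Sections 1.1 and 9.1 treat them differently.

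- **ORR:** "Overall response rate according to the International Working Group (IWG) (see Appendix B"). No separate criteria are given for AML.
- **Hematologic response:** "Hematologic response/improvement by IWG 2006 criteria for MDS patients and the IWG 2003 criteria for AML". Here the two diseases get different criteria.

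Section 9.4.1 defines ORR as "complete response and partial response based on International Working Group definition", without a year. Sections 9.4.1.1 and 9.4.3 both state the analysis as follows: "The response rates, including ORR and hematologic response by IWG 2006 criteria will be estimated", by an exact binomial method with a 95% interval. The estimate combines patients treated at the RP2D in escalation with the expansion cohort. IWG 2003 does not appear in either analysis section.

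Appendix B is headed with reference 1 alone, the 2006 IWG paper on myelodysplasia. Reference 2, the 2003 IWG paper on AML, is cited but its criteria are not reproduced anywhere. Section 5.1 makes sAML one of two routes into the trial and sets no quota or expected share.

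**The concern.** The plan accepts in its endpoint list that AML needs its own criteria, and then loses this in the analysis section. Anyone scoring hematologic response in an sAML patient meets two conflicting instructions. Anyone scoring ORR in that patient finds only an MDS table.

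That table fits AML poorly in two places. Its partial remission is a relative fall in blasts with no absolute limit on what remains. Its numeric progression bands end at blast levels that a leukaemia patient can exceed at baseline.

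At stake is what the pooled ORR means. It is the main efficacy figure from the expansion cohort and is read beside the 45% that the plan calls clinically meaningful. If sAML responses come from a scale written for another disease, the pooled rate is hard to interpret as response in sAML. PFS is affected too, since it needs a progression definition.

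**Working it through.** **1. Which criteria apply to whom**

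| Item | MDS | sAML |
|---|---|---|
| Hematologic response, endpoint lists (1.1, 9.1) | IWG 2006 | IWG 2003 |
| Hematologic response, analysis (9.4.1.1, 9.4.3) | IWG 2006 | IWG 2006 (only criteria named; pooled) |
| ORR, endpoint lists (1.1, 9.1) | Appendix B = IWG 2006 | Appendix B = IWG 2006 |
| ORR, analysis (9.4.1, 9.4.1.1, 9.4.3) | IWG | IWG, no AML branch |

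Rows 1 and 2 disagree for sAML. Rows 3 and 4 do not disagree with each other; both leave out AML criteria.

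**2. Partial remission in Appendix B**

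The marrow rule is "Bone marrow blasts decreased by ≥ 50% over pretreatment but still > 5"%. The largest residual blast percentage that satisfies it is therefore 0.5 × baseline:

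- baseline 40%: up to 20%
- baseline 60%: up to 30%
- baseline 80%: up to 40%

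The marrow fall is not sufficient. Any CR criterion that was abnormal before treatment must also be met: hemoglobin at least 11 g/dL, platelets at least 100 × 10⁹/L, neutrophils at least 1.0 × 10⁹/L and 0% peripheral blasts. The response must last at least 4 weeks, unless further protocol therapy such as consolidation starts sooner; a footnote then allows the category reached at that time.

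**3. Progression in Appendix B**

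The highest numeric band is "20%-30% blasts: ≥ 50% increase to > 30% blasts". A patient starting above 30% has no band. These rows carry no baseline limit and still apply:

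- Failure, which includes a rise in marrow blast percentage
- Relapse after CR or PR, which includes return to the pretreatment blast percentage
- the progression items on granulocytes, platelets, hemoglobin and transfusion dependence

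**4. The plan's own figures**

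The two-sided exact 95% interval runs from the 0.025 quantile of Beta(x, n − x + 1) to the 0.975 quantile of Beta(x + 1, n − x). With n = 13:

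- x = 13 × 0.45 = 5.85: 18.4% to 73.9% (plan: 18-74%)
- x = 13 × 0.50 = 6.5: 22.1% to 77.9% (plan: 22-78%)

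Both reproduce. No stated figure is wrong.

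**5. Weight of one patient**

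n is 3 + 10 = 13 or 6 + 10 = 16. One patient is 1/13 = 7.7 points or 1/16 = 6.25 points. At n = 13:

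- 6/13 = 46.2% (19.2% to 74.9%)
- 5/13 = 38.5% (13.9% to 68.4%)
- 4/13 = 30.8% (9.1% to 61.4%)

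**6. Illustration on assumed inputs**

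Let s be the sAML share and q the proportion of sAML patients counted as responders only through the MDS-scale PR. The documents give neither. The expected shift in pooled ORR is 100 × s × q points:

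- s = 0.25, q = 0.05: 1.25 points
- s = 0.50, q = 0.10: 5 points
- s = 0.75, q = 0.20: 15 points

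This shows scale only; it is not an estimate.

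**The case against.** Several points on the other side are sound.

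- A reader might infer that the ORR analysis contradicts the ORR endpoint. It does not. IWG 2003 is named only for hematologic response, and the ORR endpoint points to Appendix B for everyone. The phrase on IWG 2006 in 9.4.3 may even qualify hematologic response alone. For ORR the defect is a missing AML definition; the contradiction is confined to hematologic response.
- A reader might infer that about half the patients will have sAML. The documents list two groups and give no share.
- A reader might infer that blast progression is undefined above a 30% baseline. What is missing is a numeric band; the other rows in step 3 remain usable.
- A reader might infer that persistent leukaemia will readily be counted as response. The blood criteria, absence of peripheral blasts and duration rule limit how often this happens, and the documents do not show how often a patient with 30% marrow blasts would meet them.
- The weight of one patient is the same for any misclassification. Crossing 45% triggers no decision: ORR is a preliminary estimate with no null test, and its stated interval is 18-74%.
- IWG 2003 is not reproduced, so nobody working from these documents can show that a given patient would be classed differently.

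These points limit the size of the problem. They do not remove the conflict on hematologic response, nor the absence of AML criteria for ORR in a trial that enrols AML.

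**Conclusion.** The point holds in two parts.

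1. Sections 9.4.1.1 and 9.4.3 contradict Sections 1.1 and 9.1 on hematologic response in sAML.
2. ORR has only an MDS definition although sAML patients enter the pooled estimate. On that definition PR has no ceiling on residual marrow blasts, and the numeric progression bands stop at a 20%-30% baseline.

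That the 2006 scale applies to sAML for ORR is read from the Appendix B reference, the pooling and the lack of an AML branch; no sentence says it outright. One patient is worth 7.7 points at n = 13. The number of patients affected, and hence any shift in ORR, cannot be established. Because ORR is secondary and descriptive, the consequence is for interpretation. The text should be corrected before responses are scored, but the design does not fail because of it.

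**What to change.** - In 9.4.1.1 and 9.4.3, align hematologic response with Sections 1.1 and 9.1: IWG 2006 for MDS and MDS/MPN, IWG 2003 for sAML.
- Apply the same assignment by disease to ORR (CR + PR under each patient's own criteria) and to the progression definition used for PFS. Carry this into the ORR line of Sections 1.1, 3 and 9.1.
- Add the reference 2 criteria to Appendix B as a second table.
- Report CR and PR separately by disease group, alongside the pooled ORR.
- Progression is also an off-study criterion (Section 6.1.3.1) and ends AE reporting (Section 8.4.5). Those passages must be reconciled with whatever definition is adopted.

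The cost is protocol wording and one appendix table. The marrow and blood-count assessments are already scheduled, so no new procedure is needed. The sAML contribution to ORR may change, by an amount that cannot be predicted from the documents.
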